7.5. Visit Windows

Visit windows will be used to associate assessments with a scheduled visit for summarizing data by visit.

Visit windows are relative to Cycle 1 Day 1. In Cycle 1, the visit window for visits within Cycle 1 is a ± 1 -day window to the scheduled date, and the visit window is a ± 3 -day window to the scheduled date for visits in Cycle 2 or after. The post-treatment follow-up period starts after the final dose of study treatment (exicorilant or enzalutamide, whichever is latest). The

30-day–posttreatment follow-up visit will occur 30 days after the final dose of study treatment (exicorilant or enzalutamide, whichever is latest). Long-term phone follow-up for overall survival (ie, the date and cause of death, and post-treatment information) will continue every 4 months (± 10 days) until the study endpoints are met or 2 years from the date that the last patient enrolls in the study (whichever is later).

All data will be tabulated per the evaluation visit as recorded on the eCRF, even if the assessment is outside of the visit window.

For efficacy assessments and AEs, data from both planned visits and unscheduled visits will be assessed and summarized. For all other by-visit safety assessments, unscheduled visits will be mapped into analysis visit windows as shown below ([Table 2](#)). If more than one assessment occurs within a given analysis visit window, (1) the planned visit will be always used in summaries for the given visit; (2) if all visits are unscheduled visits, the assessment closest to the target date will be used.

Table 2: Analysis Visit Windows for Safety Assessment

Visit Name	Start Day	Target Day	End Day
Cycle 1 Day 1	-28 or -7 or -1 ^a	1	4
Cycle 1 Day 8	5	8	11
Cycle 1 Day 15	12	15	18
Cycle 1 Day 22	19	22	25
Cycle 2 Day 1	26	29	36
Cycle 2 Day 15	37	43	50
Cycle 3 Day 1	51	57	71
Cycle 4 Day 1	72	85	99
Cycle 5 Day 1	100	113	127
Cycle 6 Day 1	128	141	155
Cycle 7 Day 1	156	169	183
Cycle 8 Day 1	184	197	211
Cycle 9 Day 1	212	225	239
Cycle 10 Day 1	240	253	267
...
EOT		Study day of last dose of study drug	
EOT + 30 Days	Study day of last dose of study drug + 1	Study day of last dose of study drug + 30	Study day of last dose of study drug + 75
Post Treatment Follow-up 2	Study day of last dose of study drug + 76	Study day of last dose of study drug + 150	Study day of last dose of study drug + 210
...

^a The Lead-In Period only applies to patients in Dose-Determination Phase Segment 1 and patients in the Expansion Phase Food-Effect Subcohort. Lead-in duration is 28 days in Dose-Determination Phase Segment 1, and 7 days for patients in the Expansion Phase Food-Effect Subcohort. The start day of cycle 1 day 1 is -28 for Dose-Determination Segment 1, -1 for Dose-Determination Segment 2, and -7 for Expansion Phase.

8. Statistical Methods

Analysis populations will be specified for each of the endpoints.

8.1. Patient Disposition

Patient populations will be summarized for all patients enrolled and will include the number and percentage of patients in each analysis population.

All patients who discontinue with the study will be included in a data listing. For each treatment group and overall, disposition summaries will present the number of enrolled patients, number of patients completing the study per protocol, and the number of patients terminating the study early by primary reason for discontinuation. Primary reason for discontinuation of treatment, including any of the following, will be summarized:

- Disease progression.
- AE(s).
- Investigator decision.
- Patient withdrawal of consent for treatment.
- Patient withdrawal of consent from study.
- Protocol non-compliance.
- Patient Died
- Unknown / lost to follow-up
- Other

Counts and percentages of patients who complete the study and those who discontinue for any of the following reasons will also be calculated:

- Death
- Lost to follow-up
- Study Terminated by Sponsor
- Withdrawal of consent
- Other

8.2. Protocol Deviations

Any noncompliance with the clinical trial protocol, good clinical practice (GCP), or manual of procedures (MOP) requirements, either on the part of the patient, the Investigator, or study site staff, will be considered a protocol deviation.

Protocol deviations will be categorized as important or other according to the protocol deviation specification document. Important protocol deviations that occur during the study will be summarized by deviation category by treatment regimen dose group/arm. A listing of all protocol deviations will be provided before database lock. This list will be maintained

cumulatively on the protocol deviation log and filed in the electronic Trial Master File (eTMF) at the end of the study.

8.3. Demographic Characteristics

The following patient characteristics collected at screening for the Safety population will be presented in data listings and summarized by treatment regimen and overall:

- Age at informed consent (continuous and categorical variable: <65, and ≥65)
- Sex
- Race
- Ethnicity
- Country/Territory of birth
- History of tobacco and alcohol use

8.4. Disease Characteristics and Previous Therapies

Prior cancer treatments include surgeries, systemic and radiation therapies will be summarized for ITT population.

Prior Anticancer Therapy for Prostate Cancer: All prior anticancer therapies received, and whether ongoing, will be listed by date of first dose. A summary table will be provided by treatment regimen dose group/arm and overall for number of patients reporting at least one prior anticancer therapy, prostate cancer disease status, best response achieved, and reason for discontinuation of therapy (toxicity, disease progression, or Other) and related information. Prior anticancer therapy for prostate cancer will also be summarized by following categories:

- Chemotherapy
- Immunotherapy
- Androgen deprivation therapy (ADT)
- Anti-androgens
- Secondary hormone therapy (excluding anti-androgens)
- Bone-targeted therapy
- Other

Prior Anticancer Therapy for Non-Prostate Cancer: A listing will display all entries for prior anticancer therapies received for non-prostate cancer. Summary statistics will be presented

for cancer type, administrative setting, best response, and reason for discontinuation for prior therapy.

Prior Radiotherapy: A listing will display all entries for prior radiotherapies received by date of first dose. For patients who received at least one prior radiotherapy, its indication, site, administrative setting, modality and total dose will be summarized by treatment regimen dose group/arm and overall.

8.5. Medical History

Non-Cancer Medical History:

As noted on the non-cancer medical history eCRF, relevant significant medical conditions will be presented in a listing and summary table. Verbatim terms will be coded using the MedDRA (version 20.1 or later) and ordered by system organ class and preferred term. At each level of summation (system organ class, preferred term), patients reporting more than one medical condition will be counted only once.

Cancer Medical History – Non-Prostate Cancer:

Patient history of non-prostate cancer, including type, date of original diagnosis, and stage at original diagnosis will be listed. A summary table will include counts and percent for type of cancer (in descending order of frequency) and stage at original diagnosis.

Prostate Cancer Medical History:

Details of prostate cancer medical history recorded on the eCRF, including total Gleason score, tumor histology at diagnosis, clinical tumor stage, clinical regional lymph nodes stage, and distant metastasis at initial prostate cancer pathological diagnosis will be listed and summarized.

Prior Prostate Cancer Procedures/Surgeries: A listing will be provided for all prior procedures and surgeries for prostate cancer.

Prior Cancer Panel/Molecular Profiling Results: Analysis may be described in the Biomarker SAP.

8.6. Prior and Concomitant Medications and Therapies

Any concomitant medication used by patients will be recorded on eCRF. Indication for use, whether taken for medical history or AE, start and end date, ongoing, dose, dose formulation, frequency, and route of administration will be noted. Medications are considered concomitant if exposure occurs during the treatment-emergent period. Medications missing both start and stop dates, or medications having a start date prior to the first dose of study product and missing the stop date, or medications having a stop date on or after the last dose of study product and missing start date will be counted as concomitant.

A patient reporting use of the same medication more than once will be counted once in the calculation of the number and percentage of patients who received that medication.

Verbatim terms from the eCRF will be mapped to Anatomical/Therapeutic Chemical (ATC) drug class (level 4) and generic drug names using the WHO Drug Dictionary (WHODD) Global B3 September 2019 coding dictionary.

For each treatment regimen dose group/arm, a listing will display all entries for medications received by a patient, ordered by “Start date”. The listing will display the recorded term from the eCRF and, the ATC level 2 class (therapeutic subgroup) and the preferred/generic drug name.

A summary table will be organized to display the therapeutic subgroup (level 2) and preferred/generic drug name. It will include counts and percentages of patients who reported using at least one medication in each therapeutic subgroup by treatment regimen dose group/arm and overall.

A data listing will be provided for all concomitant procedures and/or surgeries.

Concomitant radiotherapy, blood transfusions, and subsequent anticancer therapies received will be listed and summarized by treatment regimen dose group/arm and overall.

8.7. Treatment Exposure and Compliance

All recorded information on oral dosing of exicorilant and enzalutamide, including dose level, frequency, and reason for dose interval changes will be presented in a data listing by date of administration. Note that daily dose was printed on the CRF, yet the data collected were dose level. To calculate the daily dose, we multiply the dose level with frequency. For the frequency of BID, the multiplier is 2. That is, daily dose equals to the dose level times 2. For the frequency of QD, the multiplier is 1. That is the dose level is the same as the daily dose.

A table by treatment regimen dose group/arm and overall will provide summary statistics on the following:

1) Number of Cycles of Treatment:

The number of cycles for each study drug will be presented based on the last visit when the patient received treatment with non-zero and non-missing dose. The number of cycles for each study drug will be calculated as duration of exposure in weeks/4.

2) Duration of Exposure:

The duration of exposure for each study drug will be presented in weeks and calculated as (the date of last non-zero and non-missing dose of study drug before drug discontinuation - the date of the first dose of study drug + 1)/7. Please note that if a patient had a lead-in period of a study medication, then the date of first dose for that study medication is the date of first dose in the lead-in period. If no lead in period, then start date of study drug is Cycle 1 Day 1.

3) Total Dose Received:

The total dose received for each study drug will be the sum of the actual dose administered during the duration of exposure. For subjects where their dose received is either zero or missing prior to drug discontinuation, a received dose of zero is included in the total dose received derivation.

4) Total dose expected:

The total dose expected is calculated for each study drug. The expected drug dosing schedule and the protocol-specified dose escalations, if any, is used in combination with the actual date and dose of study drug administration to calculate the total dose expected.

For Segment 1 of the Dose Determination Phase, the starting dose for both drugs in each cohort is its expected dose level.

For Segment 2 of the Dose Determination Phase, a protocol-specified dose escalation is expected for patients randomized to the Arm A group.

- The expected dose of exicorilant for Segment 2 Arm A patient is 240 mg QD from Cycle 1 Day 1 to Cycle 1 Day 14, 280 mg QD from Cycle 1 Day 15 to Cycle 1 Day 28, and 320 mg QD thereafter.
- The expected dose of exicorilant for Segment 2 Arm B patient is 240 mg QD.
- The expected dose of enzalutamide for Segment 2 patient is patient's currently tolerated dose through the Screening Period and the initiation of exicorilant.

5) Relative dose intensity:

Relative dose intensity is calculated for each study drug as the total dose received divided by the total dose expected, multiplied by 100.

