5.4.2 Dose-Determination Phase Segment 2 (Double-Blind)

In Segment 2, all patients will start treatment with CORT125281 240 mg QD on Cycle 1 Day 1. Patients will continue on their current dose of enzalutamide during the Screening Period and at the initiation of CORT125281. Beginning on Cycle 1 Day 16, the dose of the investigational agent will be increased in 40-mg increments every 2 weeks, as tolerated, with either CORT125281 (Arm A; N=12) to a maximum dose of CORT125281 320 mg QD or with placebo (Arm B; N=4) (Table 8). If any planned dose escalation is postponed due to transient intolerable Grade 2 toxicity or scheduling conflicts (delays not due to toxicity), the dose may be escalated within 14 days of the planned escalation.

- Arm A (N=12): CORT125281 240 mg QD under fed conditions with upward dose titration in combination with enzalutamide. CORT125281 will be increased in 40-mg increments every 2 weeks (+14-day window) based upon tolerability to a maximum dose of 320 mg QD (Table 8).
 - Cycle 1 Day 1: CORT125281 240 mg QD
 - Cycle 1 Day 16 (+14-day window): CORT125281 280 mg QD
 - Cycle 2 Day 2 to Cycle 2 Day 16 (+14-day window): CORT125281 320 mg QD

- Arm B (N=4): CORT125281 240 mg QD under fed conditions, with an increase in the number of placebo capsules every 2 weeks (+14-day window) (Table 8).
 - Cycle 1 Day 1: CORT125281 240 mg QD
 - Cycle 1 Day 16 (+14-day window): CORT125281 240 mg QD
 - Cycle 2 Day 2 to Cycle 2 Day 16 (+14-day window): CORT125281 240 mg QD

Table 8 CORT125281 Upward Dose Titration for Dose-Determination Phase Segment 2

Dose Level	Resulting CORT125281 Dosage (QD)		Open-Label Bottle (CORT125281)	Blind-Label Bottle (CORT125281 or Placebo) ^a
	Arm A	Arm B		
1 (Starting Dose)	240 mg	240 mg	6 capsules	0 capsules
+1 (First Increase)	280 mg	240 mg	6 capsules	1 capsule
+2 (Second Increase)	320 mg	240 mg	6 capsules	2 capsules

QD, once daily.

Note: The CORT125281 dose will be escalated in 2-week intervals unless there are intolerable Grade 2 toxicities, dose-limiting toxicities, or Grade 3 or greater toxicities attributed to CORT125281 (Section 5.7).

^a. Note: The blind-label bottle contains blinded capsules (CORT125281 [Arm A] or placebo [Arm B]).

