6.6 Pharmacokinetic Measures

The plasma concentration data for CORT125281, CORT125324 (metabolite of CORT125281; $K_i > 10$ μ M at the GR), enzalutamide, M2, and enzalutamide carboxylic acid (inactive metabolite of enzalutamide) will be analyzed using non-compartmental methods to obtain estimates of standard PK parameters.

- Dose-Determination Phase Segment 1

- Lead-in Period: Plasma samples will be collected over a 24-hour period on the day prior to initiating CORT125281 to determine the PK parameters of enzalutamide and major metabolites.
- Combination Treatment Period: Plasma samples will be collected to assess the PK profile of CORT125281, enzalutamide, and their major metabolites to determine steady-state CORT125281 PK parameters and to assess the effect of CORT125281 on exposure to enzalutamide.
 - Cycle 1 Day 1
 - Cycle 1 Day 22 (partial profile)
 - Cycle 2 Day 1
 - Cycle 2 Day 15 and Cycle 3 Day 1 (partial profile)
- Dose-Determination Phase Segment 2
 - Combination Treatment Period: Plasma samples will be collected to assess PK parameters of CORT125281 and enzalutamide.
 - Cycle 1 Day 15
 - Day before second dose escalation (eg, Cycle 2 Day 1 or Cycle 2 Day 15)
- Expansion Phase:
 - Food-Effect Subcohort (10 patients in the Abi-Resistant Cohort):
 - Cycle 1 Day -7 and Day 1: Plasma samples will be collected to determine CORT125281 PK parameters
 - All patients in the Expansion Phase: Plasma samples to be collected on Cycle 2 Day 1 and Cycle 3 Day 1 to determine the concentration of CORT125281, enzalutamide, and their major metabolites.

Refer to the SoAs in [Table 20](#) (Dose-Determination Phase Segment 1), [Table 21](#) (Dose-Determination Phase Segment 2), and [Table 22](#) (Expansion Phase) for the timing and frequency of all PK sample collections.

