- ^r. For patients in Dose-Determination Phase Segment 2, the patient will take their current dose of CORT125281 in the clinic on Cycle 1 Day 1, Cycle 1 Day 15, and the day before their second dose escalation (eg, Cycle 2 Day 1 or Cycle 2 Day 15). If the patient tolerates the current dose and escalation/titration of the dose occurs, the first day of the increased dose will be on the day following the study visit. For patients in the Expansion Phase Food-Effect Subcohort, enzalutamide dosing will begin on Cycle 1 Day 2.
- ^s. Record post-treatment anticancer therapies, dates of initiation, and end dates, and response.

Table 17 Pharmacodynamic Schedule of Assessments, Dose-Determination Phase Segment 1

Procedure/Assay	Tissue Source	Visit Schedule Cycle Day	Methodology; Examples of Biomarkers
ACTH, cortisol	Blood	Screening, Cycle 1 Day 1 ^a , Cycle 1 Day 15, Cycle 3 Day 1, Every 3 cycles from Cycle 3 ^b , Upon discontinuation (+7 days) of CORT125281, Disease progression ^c	Fasting sample collected between 7 a.m. to 9 a.m. Analysis of ACTH by radioimmunoassay and cortisol by mass spectroscopy by central laboratory
GC-related gene panel	Blood	Screening, Cycle 1 Day 1 ^a , Cycle 1 Day 15, Cycle 3 Day 1, Every 3 cycles from Cycle 3 ^b , Upon discontinuation (+7 days) of CORT125281, Disease progression ^c	Fasting sample collected between 7 a.m. to 9 a.m. at the same time as the cortisol and ACTH samples; mRNA expression by technologies such as NanoString
DHEA-S, androstenedione, estradiol and free and total testosterone	Blood	Screening, Cycle 1 Day 1 ^a , Cycle 1 Day 15	Fasting sample collected between 7 a.m. to 9 a.m. Analysis by mass spectroscopy by central laboratory
GR expression, ARV7, CTC enumeration, and exploratory markers	CTC	Screening, Cycle 1 Day 1 ^a ; Cycle 2 Day 1 Cycle 3 Day 1 Cycle 4 Day 1 Upon discontinuation (+7 days) of CORT125281, Disease progression ^c	Serial assessment of CTC number and biomarkers for response, prognosis, and to identify correlative markers of sensitivity, Example biomarkers include ARV7 protein immunofluorescent assay or GR IHC run on the [REDACTED] Platform
GR expression, ARV7, and exploratory markers	Paired tumor biopsies	Screening Cycle 2 Day 1 ^d	Formalin fixed, paraffin embedded tissue sample; includes IHC for GR [REDACTED] and the mRNA expression of genes involved in tumor GR-signaling, resistance, apoptosis, and metabolism

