2.3. Phase 1, Dose-Determination Segment 2 (Double-Blind)

Segment 2 of the Dose-Determination Phase is randomized and double blinded for dose titration with respect to exicorilant in combination with enzalutamide. All patients will receive exicorilant at a starting dose of 240 mg once daily (QD) under fed conditions. Approximately 20 patients will be enrolled to achieve 16 DLT-evaluable patients randomized in a 3:1 ratio to receive exicorilant in combination with enzalutamide either with the starting dose of exicorilant 240 mg QD with dose titration to 320 mg QD (N=12; Arm A) or with the starting dose of exicorilant 240 mg QD, without an increase of the active dose (N=4; Arm B). Patients in Arm B will receive placebo capsules, such that the patient, Investigators, and study team are blinded to which dose patients are receiving (ie, 240 mg QD versus 240 mg to 320 mg QD). In Segment 2, all doses of exicorilant should be taken with food.

All patients will start treatment with exicorilant 240 mg QD on Cycle 1 Day 1. Patients will continue on their current dose of enzalutamide during the Screening Period and at the initiation of exicorilant. Beginning on Cycle 1 Day 16, the dose of exicorilant will be increased in 40-mg increments every 2 weeks, as tolerated, with either exicorilant (Arm A; N=12) to a maximum dose of exicorilant 320 mg QD or with placebo (Arm B; N=4) (Table 1). If any planned dose escalation is postponed due to transient intolerable Grade 2 toxicity or scheduling conflicts (delays in escalation

not due to toxicity), the dose may be escalated within 14 days of the planned escalation.

- **Arm A (N=12):** exicorilant 240 mg QD under fed conditions with upward dose titration in combination with enzalutamide. Exicorilant will be increased in 40-mg increments every 2 weeks (+14-day window) based upon tolerability to a maximum dose of 320 mg QD (Table 1).
 - Cycle 1 Day 1: exicorilant 240 mg QD
 - Cycle 1 Day 16 (+14-day window): exicorilant 280 mg QD
 - Cycle 2 Day 2 to Cycle 2 Day 16 (+14-day window): exicorilant 320 mg QD
- **Arm B (N=4):** exicorilant 240 mg QD under fed conditions, with an increase in the number of placebo capsules every 2 weeks (+14-day window) (Table 1).
 - Cycle 1 Day 1: exicorilant 240 mg QD
 - Cycle 1 Day 16 (+14-day window): exicorilant 240 mg QD
 - Cycle 2 Day 2 to Cycle 2 Day 16 (+14-day window): exicorilant 240 mg QD

Table 1: Exicorilant Upward Dose Titration for Dose-Determination Segment 2

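### SAP 8.7 starts both Arm A dose increases one day too early in the expected exicorilant dose, so a perfectly adherent, earliest-escalating patient scores below 100% relative dose intensity

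*SAP*

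**What the plan says.** SAP 8.7 defines relative dose intensity as total dose received over total dose expected, times 100. For the expected dose in Segment 2 it states that "a protocol-specified dose escalation is expected for patients randomized to the Arm A group". It then fixes the calendar for Arm A: 240 mg once daily through Cycle 1 Day 14, followed by "280 mg QD from Cycle 1 Day 15 to Cycle 1 Day 28, and 320 mg QD thereafter". With 28-day cycles, 320 mg is expected from Cycle 2 Day 1, which is study Day 29.

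The dosing rules give other days:

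- SAP 2.3: "Beginning on Cycle 1 Day 16, the dose of exicorilant will be increased in 40-mg increments every 2 weeks". Its Arm A schedule lists the second step as "Cycle 2 Day 2 to Cycle 2 Day 16 (+14-day window): exicorilant 320 mg QD".
- Protocol 5.4.2 agrees: "Beginning on Cycle 1 Day 16, the dose of the investigational agent will be increased in 40-mg increments every 2 weeks". It gives the same Cycle 2 Day 2 earliest date for 320 mg.
- Protocol Appendix A, Table 16, footnote r, for Segment 2: "the patient will take their current dose of CORT125281 in the clinic on Cycle 1 Day 1, Cycle 1 Day 15", and also on the day before the second escalation. If the dose is then raised, "the first day of the increased dose will be on the day following the study visit".
- Protocol 6.6 lists the second Segment 2 pharmacokinetic sampling day as "Day before second dose escalation (eg, Cycle 2 Day 1 or Cycle 2 Day 15".

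SAP 13, which lists changes from the protocol's planned analyses, covers only the definitions of treatment emergence and baseline.

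**The concern.** SAP 8.7 says its expected dose follows the escalation in the protocol, but the days it prints do not. Days 15 and 29 are visit days on which an on-schedule patient takes the lower dose, yet the expected total counts the higher dose on both. The denominator of relative dose intensity is then too large, and a patient who did everything the protocol asked appears slightly under-dosed.

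The artefact falls on one arm only. Arm B is expected to take a flat 240 mg and can reach 100%, while the titrated arm cannot on the earliest schedule. The two sit side by side in an exposure table presented by arm. SAP 7.3 reports percentages to one decimal place, so the shortfall would show.

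**Working it through.** **Inputs.** Cycles are 28 days with no rest periods (protocol Table 16, note), so Cycle 2 Day 1 is Day 29 and Cycle 2 Day 2 is Day 30.

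| Dose | Expected days, SAP 8.7 | Earliest days, SAP 2.3 and protocol 5.4.2 |
|---|---|---|
| 240 mg | 1–14 | 1–15 |
| 280 mg | 15–28 | 16–29 |
| 320 mg | from 29 | from 30 |

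**Where SAP 8.7's days may come from.** Counting bare two-week blocks from Day 1 puts the steps on Days 15 and 29, as in SAP 8.7. Using the stated dates puts them on Days 16 and 30. SAP 8.7 can be reproduced only by ignoring the explicit dates.

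**Formula.** Relative dose intensity = 100 × received / expected. The patient escalates on Cycle 1 Day 16 and Cycle 2 Day 2, stays at 320 mg and misses no dose.

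- Excess from Day 15: 280 − 240 = 40 mg.
- Further excess from Day 29: 320 − 280 = 40 mg, so 80 mg in total, fixed from then on.

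Worked at Day 84, the end of Cycle 3:

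- Expected: 14×240 + 14×280 + 56×320 = 25,200 mg.
- Received: 15×240 + 14×280 + 55×320 = 25,120 mg.
- Relative dose intensity: 25,120 / 25,200 = 99.68%.

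| Last dose day | Received (mg) | Expected, SAP 8.7 (mg) | Relative dose intensity |
|---|---|---|---|
| 14 | 3,360 | 3,360 | 100.00% |
| 15 | 3,600 | 3,640 | 98.90% |
| 28 | 7,240 | 7,280 | 99.45% |
| 29 | 7,520 | 7,600 | 98.95% |
| 56 | 16,160 | 16,240 | 99.51% |
| 84 | 25,120 | 25,200 | 99.68% |
| 168 | 52,000 | 52,080 | 99.85% |
| 336 | 105,760 | 105,840 | 99.92% |

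The minimum is 98.90%, at Day 15. The figure first rounds to 100.0% at Day 506.

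**With corrected days.** Expected at Day 84 becomes 25,120 mg, equal to the dose received, so relative dose intensity is 100.0%.

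**Reach of the error.** SAP 8.8 decides DLT evaluability by the share of doses taken (at least 75%, or 63 days) and bases the DLT rates on patients and treatment time. Neither uses relative dose intensity.

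**The case against.** The strongest counter-argument concerns visit windows. Footnote r ties the increase to the day after the visit, and protocol 7.3 allows visits ±1 day in Cycle 1 and ±3 days later. If the Day 15 visit is held on Day 14 and the Cycle 2 Day 1 visit on Day 28, the steps land on Days 15 and 29, matching SAP 8.7, and the patient reaches 100%. The protocol does not say how an early in-window visit interacts with the escalation dates. Those dates, however, carry their own window, which runs forward only (+14 days). A visit window does not move a dosing date that has a stated earliest day. The reading also does nothing for a patient seen exactly on schedule, which is the case at issue.

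Second, SAP 8.7 says the expected dose is worked out in combination with actual administration dates, which might be read as flexibility. The Arm A bullet nevertheless fixes the step days and gives no rule for moving them.

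Third, permitted delays matter far more. Escalating on Days 30 and 44 gives 24,000 / 25,200 = 95.2% at Day 84, and still 24,000 / 25,120 = 95.5% after correction. This stands: the correction yields 100% only for the earliest escalator. But a delayed patient really received less than the earliest schedule provides, whereas here a patient with no departure at all is scored as under-dosed.

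The objection that the effect is negligible is largely right on size. It does not make the printed days correct.

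**Conclusion.** The concern holds. SAP 8.7 places both Arm A steps one day before the earliest date in SAP 2.3 and protocol 5.4.2, contrary to its own stated basis and without being declared as a change in SAP 13. For an adherent Arm A patient who escalates on Cycle 1 Day 16 and Cycle 2 Day 2 and is treated past Day 14, relative dose intensity is always understated: by at most 1.1 points (dosing ends on Day 15), by 0.3 points at Day 84, and by less thereafter. This assumes the forward-only escalation window governs and that the fixed days in SAP 8.7 are programmed as written.

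The matter is minor. It affects one descriptive exposure summary in one arm and leaves DLT evaluability, the DLT rates and the Data Review Committee's criteria untouched.

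**What to change.** Replace the Arm A line in SAP 8.7 with: 240 mg once daily from Cycle 1 Day 1 to Cycle 1 Day 15, 280 mg once daily from Cycle 1 Day 16 to Cycle 2 Day 1, and 320 mg once daily from Cycle 2 Day 2. Change the matching dates in the exposure program.

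The cost is one line of text and two program dates, with no new data.
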